10.3 Subject Screening

All subjects that are considered for the study should be included on the study screening log. The reason for non-eligibility, as determined by the Investigator should also be recorded on the study screening log. The screening log serves as a method for Medtronic to assess selection bias in the trial.

10.4 Prior and Concomitant Medications/Therapies

There are medication restrictions in this study that include: psychoactive medications and any medication that may have an impact on the CNS. Subjects cannot be on any psychoactive medication and be included in the study.

10.5 Subject Consent

The Investigator or designee must obtain written informed consent before any clinical study related activity takes place. Before entry into the study, the Institutional Review Board (IRB) and Medtronic-

Medtronic Business Restricted

approved ICF form, and the Health Insurance Portability and Accountability Act (HIPAA) Authorization Form (if not included within the ICF) (the US only) will be given to the parent or legal guardian of the potential subject.

The Investigator or designee will fully inform the parent or legal guardian of the potential subject of all aspects of the clinical study that are relevant to the decision to participate in the clinical study. These activities may include the rights of the child as a subject in a research project, purpose and duration of the study, requirements of the subject during the study, potential risks and possible benefits associated with participation in this study. All items addressed in the ICF must be explained. The language used shall be as non-technical as possible and must be understandable to the parent/legal guardian. The parent/legal guardian must have ample time and opportunity to read and understand the ICF, to inquire about the details of the clinical study, and to decide whether or not to participate in the clinical study. The parent or legal guardian of a potential subject will be encouraged to discuss participation in the study with their support network (family, friends). All questions about the clinical study should be answered to the satisfaction of the parent/legal guardian.

Neither the Investigator nor the investigation site staff shall coerce or unduly influence a subject and/or the parent/legal guardian to participate or to continue to participate in the clinical study. The informed consent process shall not waive or appear to waive the subject's rights.

The parent or legal guardian of the potential subject who then wishes to participate, and where the subject meets the inclusion/exclusion criteria, will be asked to sign and personally date the informed consent form on behalf of their child. Children of appropriate age will need to assent to the study and will be provided with an appropriate Institutional Review Board (IRB) approved Research Assent Form (RAF). The signed original informed consent is maintained in the Investigator's records and a copy given to the parent/legal guardian.

Medtronic will inform the Investigators whenever information becomes available that may be relevant to the subject's confirmed participation in the clinical study. The Investigator or his/her authorized designee should inform the subject's parent/legal guardian in a timely manner.

Medtronic will revise the written ICF whenever new information becomes available that may be relevant to the subject's confirmed participation in the clinical study. The revised information will be sent to the Investigator for approval by the IRB. After approval by the IRB, a copy of this information must be provided to the participating subjects, and the informed consent process, as described above, needs to be repeated.

10.6 Enrollment

A subject is considered enrolled when the consent process has been finalized. The date the subject (or the subject's authorized/designated representative or guardian) signed the IC and Data Protection Authorization, as required by law, must be documented in the subject's medical records. A log of all

Medtronic Business Restricted

subjects enrolled in the study should be maintained. Enrollment can be a stand-alone visit or can occur on the same day as the baseline visit. Once consent is obtained, report adverse events/deaths, study deviations and subject exits as they occur.

10.7 Baseline

Once ICF is signed, the following will be obtained:

- Demographics (race, ethnicity, sex, height, weight, skin tone,)
- Medical history, including diagnosis for surgery and the American Society of Anesthesiologist (ASA) physical status classification system, is used to evaluate the degree of a patient's "sickness" or "physical state." Only subjects with ASA Physical status I, II or III will be enrolled
- Concomitant Medications, including the history of prescription and over the counter medication, will be carefully noted and recorded within 1 month before the surgery. Medication name, indication for use, dose, frequency, route of administration start/stop date
- Cardiovascular Variables - Heart Rate, Systolic, mean, and Diastolic Blood Pressures, Respiratory Rate, Oxygen Saturation (SpO₂)

10.8 Randomization and Treatment Assignment

Prior to Randomization, 2 - 4 subjects from each site will be consented and enrolled. The data will be used to train on the new technology use, and to review the quality of the data collection, refer to *Section 10.2*.

Subjects are eligible for randomization assignment after study enrollment and verification of eligibility criteria. Subjects will be randomized in a 1:1 fashion to the BIS™ group or standard practice group using the RDC electronic system. Randomization schedules will be created by a Medtronic statistician, and randomization assignments will be automatically populated on the Randomization e-CRF after subject consent and eligibility verification have been entered in RDC. The randomization schedule will be stratified by age group and the study site to ensure 1:1 randomization within each study site.

10.9 Surgical Procedure and Data Collection

The surgical procedure will be conducted per Standard of Care (SOC). Subjects are being recruited with a planned maintenance time of 30 minutes or greater. If the subject's maintenance time is less than 25 minutes, the data will continue to be collected, but will not be included in the final data analysis and the subject will be replaced by an additional enrolled subject.

10.9.1 Prior to Induction

Prior to induction, subjects may be pre-medicated with Midazolam (Versed) per institutional guidance. The subject taken into the operating room, and anesthesia delivery system will be applied per institutional guidance.

10.9.1.1 BIS™ Sensor Application

Prior the induction of anesthesia, all subjects will have an age-appropriate BIS™ sensor. The sensor, BIS™ pediatric or BIS™ QUATRO Sensor, will be selected by the clinician based on the size of the forehead and space available on the forehead. The sensor will be placed on the forehead after cleaning the site with an alcohol wipe per the IFU recommendation. The sensor type will be captured on eCRFs.

10.9.1.2 Pulse Oximeter Sensor Application

The age-appropriate pulse oximeter sensor will be applied to the subject per sensor IFU. A left or right index finger is the preferred sensor site. Alternatively, the sensors can be applied to a smaller finger, thumb, or big toe. The sensor type, position and side will be recorded on the eCRF.

If the subject is uncooperative when awake, the BIS™ sensor will be placed after adequate sedation has been achieved with the use of pre-medication drugs.

The choice of pre-medication, dose, and time of administration will be determined by the site anesthesiologist and will not be altered for the study, but the use of these drugs will be recorded on the eCRF.

10.9.2 Induction

Anesthesia will be induced with sevoflurane alone, or a combination of sevoflurane and nitrous oxide (N₂O) in 100% oxygen in both groups. If the nitrous oxide is used, it will be discontinued after the placement of a tracheal tube or laryngeal mask (LMA), or another airway management. If necessary, a neuromuscular blocking agent will be used to facilitate endotracheal intubation. The choice of medication, dose, and time of administration will be determined by the site anesthesiologist and will not be altered for this study, but the use of these drugs will be recorded on the eCRFs. If the subject is in need of a regional block for pain management following the procedure, this block should be placed once skin closure is complete and prior to extubation. This block cannot be placed prior to skin closure. Subjects with the planned use of any regional anesthesia are excluded from this study, however if any regional anesthesia becomes necessary for the subject during the course of the surgical procedure, data will continue to be collected on the subject, however the data will not be included in the data analysis and the subject will be replaced by an additional enrolled subject. The use of dexmedetomidine (Precedex) is prohibited from being used in this study. If it becomes necessary to use this medication during the course of the surgical procedure, data will continue to be collected on the subject, however the data will not be included in the data analysis and the subject will be replaced by an additional enrolled subject.

10.9.3 Maintenance

10.9.3.1 Training Group

A training group, comprising of the first 2 - 4 subjects at each site will be enrolled to train the site team on the new technology and to determine the quality of data collection before randomization.

Sevoflurane administration will be at the discretion of the anesthesiologist using clinical signs and cardiovascular changes to adjust anesthetic concentration. The end-tidal sevoflurane concentrations will be continuously recorded. Fentanyl, propofol, and/or morphine will be administered at the discretion of the anesthesiologist for example, morphine at 1.5 mcg/kg at induction and 0.75 mcg/kg every 30 minutes in accordance with usual clinical indications.

For the SP group, sevoflurane, fentanyl, propofol, and/or morphine will be administered at the discretion of the anesthesiologist for example, fentanyl and morphine at 1.5 mcg/kg at induction and 0.75 mcg/kg every 30 minutes in accordance with usual clinical indications.

The clinician will be blinded to the BIS™ values, and the BIS™ value is not used to guide the conduct of the anesthetic. The SQI number will be visible to the anesthesiologist during the case to capture a good quality signal. The details on SQI monitoring will be provided to the study site.

10.9.3.2 Standard Practice Group

In this group, sevoflurane administration will be at the discretion of the anesthesiologist using clinical signs and cardiovascular changes to adjust anesthetic concentration. The end-tidal sevoflurane concentrations will be continuously recorded. Fentanyl propofol, and/or morphine will be administered at the discretion of the anesthesiologist, for example, morphine at 1.5 mcg/kg at induction and 0.75 mcg/kg every 30 minutes in accordance with usual clinical indications.

The clinician is blinded to the BIS™ values, and the BIS™ value is not used to guide the conduct of the anesthetic. The SQI number will be visible to the anesthesiologist during the case to capture a good quality signal. The details on SQI monitoring will be provided to the study site.

10.9.3.3 BIS™ Guided Group

In the BIS™ group, sevoflurane will be adjusted to achieve a target BIS™ values of 45 – 60 during maintenance of anesthesia and BIS™ values of 60 – 75 beginning of skin closure. Subjects with BIS™ values that are outside of the specified range of 45 – 60 during maintenance of anesthesia for >35% of the maintenance duration will be considered a protocol deviation and the subject will be excluded from the final data analysis and will be replaced by an additional subject. The excluded subject will continue to be monitored for any safety events and the clinical will ensure that medical care is provided should a safety event occur. Data from the excluded subject will be acknowledged in the final study report but will not be

included in the primary statistical analysis. The exception to this exclusion is any data that is outside of the specified range of 45 – 60 as a result of the anesthesiologist titrating medications as a result of clinical signs or cardiovascular changes defined above. Additionally, data points will be excluded if significant artifact is present or if the sevoflurane concentration or BIS™ value is missing.

At the completion of the surgery, and after confirmation of the return of neuromuscular function, sevoflurane will be discontinued, and discontinuation time will be recorded, and as applicable, extubation will be performed when the patients demonstrate the purposeful movement, facial grimace, or eye-opening to jaw thrust.

10.9.4 Monitoring and Cardiovascular Variables

Monitors for the collection of variables such as pulse oximeter, non-invasive blood pressure (NIBP), electrocardiography, and skin temperature will be applied per institutional guidance. The standard monitoring procedures will be conducted per institutional recommendation and are not being mandated by the protocol. The de-identified digital copies of these files will be provided to Medtronic as available. Pre-surgical Cardiovascular variables (heart rate [HR]; systolic and diastolic blood pressure [BP] including hypotension; oxygen saturation; and temperature), and BIS™ (for the BIS™ group) will be recorded at baseline preferably before administering any pre-medication or sedatives. Cardiovascular variables will be monitored during the surgery, and any abnormal cardiovascular parameters and times will be recorded in the medical record. The de-identified digital copies of these files will be provided to Medtronic as available.

10.9.5 Event Markers and Assessments

During the case, the time of events listed below will be recorded.

The end-tidal anesthetic gas concentration will be time-locked to the BIS™ system recordings. End-tidal sevoflurane, oxygen, and nitrous oxide concentrations will be downloaded from the anesthetic monitoring device, and de-identified digital copies will be provided to Medtronic.

Time and values of BIS™, ET_{SEVO} concentration (%) and other medication, FiO2(%) and EtO2(%), EtCO2(%) will be recorded at the following time intervals:

- Baseline
- Study start
- At IV placement, as applicable
- Start of induction
- Start of N₂O, as applicable
- Start of sevoflurane
- At Anesthesia Airway Management (AAM)
- AAM change (including type of AAM)
- At any airway reflex (coughing, choking, layngospasm)
- Every 15 min after airway management
- At all drug administration (as applicable)
- N₂O off (as applicable)
- Start of the surgery/procedure
- Skin incision, if applicable
- End of surgery/procedure (or skin dressing or cast or splint applied or abdominal block)
- Skin closure, if applicable
- Sevoflurane off
- Termination of all anesthesia
- Extubation
- Physician Awakening subject, if applicable
- Time of emergence (if occurs in OR)
- End of study (removal of device)
- 15 min post dexmedetomidine administration, if applicable
- Time moved to PACU

Any time end-tidal sevoflurane concentration (ET_{SEVO}) is increased or decreased or opioid or other medication is given, the event and time will be marked on the eCRFs. Also, if any changes to the dose or administration regimen are needed, these changes will be noted on the eCRF.

10.9.6 Recovery

Subject recovery will be continuously after the termination of anesthesia for presence of coughing, choking, laryngospasms, and emergence.

Emergence is defined as the time when any of the following first occurred:

- eyes open spontaneously,
- crying or phonating, or
- purposeful movements.

The time of emergence, time subject moved to PACU, and time of readiness for discharge will be recorded. The time of these assessments will be captured in medical records, source, and recorded on the eCRFs.

All subjects will be assessed at 15-minute intervals:

- Pediatric Anesthesia Emergence Delirium (PAED)
- Wong-Baker FACES Pain Scale (when subject is awake)
- PACU discharge readiness - Modified Aldrete Score

PAED, Wong-Baker FACES Pain Scale, and Modified Aldrete Score data will be recorded in source every 15 minutes. Raw data but total scores for the highest amount of delirium from the PAED, the highest amount of pain from the Wong-Baker FACES Pain Scale and the least ready for discharge Modified Aldrete Score raw data will be entered in to the CRF. The final raw data and total scores for the PAED, Wong-Baker FACES Pain Scale and Modified Aldrete Scale will be entered into the eCRF.

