	
8) Taking any medications that may have an impact on the Central Nervous System (CNS)
 
9) Planned use of any regional anesthesia; a local field block is not included in this exclusion and can be used at the discretion of the anesthesia provider
 
10) Planned use of dexmedetomidine (Precedex)
 
11) Refusal to participate in the study

Study Procedures and Assessments	
BIS™ Group:
 
Baseline/Enrollment Visit:
 
• Informed Consent• Review of Inclusion/Exclusion• Demographics• Medical History• Pre-operative vitals obtained in pre-operative holding 
Procedure:
 
• Randomization: Prior to Procedure• Induction and Maintenance:• BIS™ sensor positioning and validation of appropriate impedance of electrodes• Clinical Anesthesia Assessment including incidence of:
• Movement• Grimacing• Eye opening• Tearing• Sweating• Mydriasis• Cardiovascular changes• End of Procedure:
• Collection of BIS™ sensor placement, monitoring of cardiovascular variables, event markers and assessments• Recovery:

- Anesthesia Airway management
- Collection of incidents of post- op nausea
- Pediatric Anesthesia Emergence Delirium (PAED)
- Wong-Baker FACES Pain Rating Score when subject is awake
- Time of PACU Discharge

SP Group:

Baseline/Enrollment Visit:

- Informed Consent
- Review of Inclusion/Exclusion
- Demographics
- Medical History
- Pre-operative vitals obtained in pre-operative holding

Procedure:

- Randomization: Prior to Procedure
- Induction and Maintenance:
- BIS™ sensor positioning and validation of appropriate impedance of electrodes
- Clinical Anesthesia Assessment including incidence of:
 - Movement
 - Grimacing
 - Eye opening
 - Tearing
 - Sweating
 - Mydriasis
- Cardiovascular changes
- BIS™ monitor concealing: done to ensure that the clinician is blinded to the BIS™ values and that the BIS™ value is not used to guide the conduct of the anesthetic. The signal quality index (SQI) number will be visible to the anesthesiologist during the case to capture a good quality signal. The details on SQI monitoring will be provided to the study site.

- End of Procedure:
 - Collection of BIS™ sensor placement, monitoring of cardiovascular variables, event markers and assessments
- Recovery:
 - Anesthesia Airway management
 - Collection of incidents of post- op nausea
 - Pediatric Anesthesia Emergence Delirium (PAED)

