4.1.3.2. Sponsor Supported Studies

The Effect of Bispectral Index Monitoring on Anesthetic Use and Recovery in Children Anesthetized with Sevoflurane in Nitrous Oxide

A prospective, randomized, observer-blinded study was designed to evaluate the effect of BIS™ monitoring on anesthetic use and recovery characteristics in pediatric patients [12]. Two hundred forty (240) patients were enrolled in the study. During a baseline phase before starting randomization, data of

Medtronic Business Restricted

38 patients were collected “historical controls.” These control patients were anesthetized according to standard institutional practice.

Two hundred two (202) patients age 0–18 years were randomized into one of two groups: standard practice (SP) and BIS™ guided (BIS™). Patients age 0–3 years, undergoing inguinal hernia repair (IH), and patients age 3–18 years, undergoing tonsillectomy and/or adenoidectomy (TA), were selected, **Table 1**. All patients were anesthetized with sevoflurane in 60% N₂O/O₂.

In the BIS™ group, anesthetic delivery was adjusted to achieve a target BIS™ values of 45–60 during maintenance and 60–70 during the last 15 minutes of the procedure.

Table 1: Demographic Data (mean ± SD)

	Control	SP	BIS
Infants (age 0–6 mo), hernia repair			
Number	8	28	32
Sex (M/F)	5/3	23/5	27/5
Age (yr)	0.2 ± 0.1	0.2 ± 0.1	0.2 ± 0.1
Weight (kg)	4.8 ± 1.0	5.1 ± 1.6	5.5 ± 1.6
Duration of Surgery (min)	26.2 ± 7.4	32.0 ± 17.6	30.1 ± 14.5
Infants and small children (6 mo–3 yr), hernia repair			
Number	11	34	33
Sex (M/F)	7/4	29/5	28/5
Age (yr)	1.8 ± 1.1	1.9 ± 1.0	2.2 ± 1.0
Weight (kg)	11.5 ± 3.6	11.9 ± 2.8	13.3 ± 3.0
Duration of Surgery (min)	20.8 ± 12.0	25.7 ± 11.8	24.8 ± 14.9
Children (age 3–18 yr), tonsillectomy and/or adenoidectomy			
Number	19	35	40
Sex (M/F)	10/9	23/12	26/14
Age (yr)	5.9 ± 2.0	6.1 ± 2.6	6.7 ± 2.5
Weight (kg)	24.8 ± 9.5	27.7 ± 14.7	26.9 ± 10.6
Duration of Surgery (min)	28.1 ± 14.2	33.2 ± 20.3	27.7 ± 17.1

SP = Standard Practice group; BIS = Bispectral Index group

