10.9.6.4 Modified Aldrete Score

End of surgery to post-anesthesia care unit (PACU) discharge readiness will be assessed using the Modified Aldrete Score that examines the following five criteria: motor activity, respiration, blood pressure, consciousness, and color [15, 16]. Before a subject can be safely discharged from the PACU, a score of 12 out of 16 points based on the PACU standard discharge criteria will be achieved. The time and score of PACU discharge readiness will be recorded. The scale is included in **Appendix C**.

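### Recovery scorers are not masked to arm, which leaves time to PACU discharge readiness and the PAED comparison open to observer bias

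*Protocol*

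**What the plan says.** **Concealment.** For the standard-practice (SP) arm, Protocol 10.9.3.2 states: "The clinician is blinded to the BIS™ values, and the BIS™ value is not used to guide the conduct of the anesthetic". The synopsis gives the purpose of concealing the monitor: "done to ensure that the clinician is blinded to the BIS™ values and that the BIS™ value is not used to guide the conduct". The training group has the same concealment (10.9.3.1) but is neither randomized nor analysed. In the BIS arm the anesthetist has to see the value: "In the BIS™ group, sevoflurane will be adjusted to achieve a target BIS™ values of 45 – 60 during maintenance of anesthesia" (10.9.3.3).

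**Recovery scoring.** Protocol 10.9.6 says "All subjects will be assessed at 15-minute intervals" and lists PAED, Wong-Baker and Modified Aldrete. On readiness, 10.9.6.4 adds: "The time and score of PACU discharge readiness will be recorded". Sections 10.9.6 to 10.9.6.4 name no scorer for Modified Aldrete or PAED and contain no masking rule. The SAP has none either.

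**How the results are used.** Protocol 14.1 and SAP 7.9 test three secondary endpoints by Holm-Bonferroni once the primary is met: time to emergence, time to PACU discharge readiness and time to extubation. PAED is summarized descriptively and compared between arms. SAP 7.5 says that no multiplicity adjustment is made. That conflicts with SAP 7.9, but readiness is tested under either reading.

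**The earlier study.** Protocol 4.1.3.2 introduces the study behind the BIS target ranges with: "A prospective, randomized, observer-blinded study was designed to evaluate the effect of BIS™ monitoring on anesthetic use and recovery characteristics".

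**The concern.** Hiding the BIS number from the SP anesthetist protects the contrast between the two ways of giving sevoflurane. It does nothing for the measurement of recovery. The BIS-arm anesthetist knows the arm, and the plan does not stop that knowledge from reaching whoever scores the child in the PACU.

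This matters most for time to discharge readiness. Several Modified Aldrete items in Appendix C are an observer's rating (consciousness, movement, need for airway assistance). Faster recovery is also the direction in which the background section leads readers to expect a benefit. A modest tendency to sign BIS children off sooner would look like a treatment effect on a formally tested endpoint. PAED is an observational scale too, so the same applies to its comparison, though that is descriptive.

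**Working it through.** **1. Which recovery outcomes depend on a PACU scorer**

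| Outcome | Role in the analysis | Who determines it, per the documents | Can PACU masking protect it? |
|---|---|---|---|
| End-tidal sevoflurane | Primary | Downloaded from the anesthetic monitor (10.9.5) | Not needed |
| Time to extubation | Holm-tested | Done on clinical signs after sevoflurane is stopped (10.9.3.3) | No |
| Time to emergence | Holm-tested | May occur in the operating room (10.9.5) | Not if it does |
| Time to PACU discharge readiness | Holm-tested | Modified Aldrete, scorer not named | Yes, for scores taken in the PACU |
| PAED | Descriptive comparison | Observational scale, scorer not named | Yes, for scores taken in the PACU |
| Wong-Baker | Descriptive | The child indicates the pain level (10.9.6.3) | Little affected |

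**2. Is PACU masking practicable on the plan's own terms?** All subjects in both arms wear the sensor (10.9.1.1). Table 5 shows no sensor use or BIS data collection in the PACU column. In 10.9.5, removal of the device is listed before the move to the PACU. Nothing planned in the PACU requires the scorer to know the arm.

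**3. The plan's own figure.** The plan gives no number on this point. Its nearest figure is power for the primary endpoint (14.2): 18 per arm per age group, difference 0.5%, SD 0.5%, two-sided 0.05.
- z = (0.5/0.5)/√(2/18) = 3.0, so power = Φ(3.0 − 1.96) = 85.1%. With the noncentral t it is 83.0%.
- The stated power of more than 80% is reproduced, and assessor masking changes none of its inputs.

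**4. Illustration with a constant shift (assumed).** Table 3 in 4.1.3.2 gives ready-to-discharge times at ages 3–18 of 26.7 ± 11.2 min (SP) and 20.0 ± 7.9 min (BIS), a difference of 6.7 min.
- SD = √((11.2² + 7.9²)/2) = 9.69 min.
- Per arm, pooling the age groups: 18 × 3 = 54.
- SE = 9.69 × √(2/54) = 1.865 min.
- With no true effect and a scoring shift of b minutes, rejection at 0.05 = Φ(b/SE − 1.96) + Φ(−b/SE − 1.96).

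| Assumed shift b (min) | b/SE | Rejection rate |
|---|---|---|
| 1 | 0.54 | 8% |
| 2 | 1.07 | 19% |
| 3 | 1.61 | 36% |
| 5 | 2.68 | 76% |

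**5. Illustration with early sign-off (assumed).** This is a simulation with no true effect and 54 per arm. Readiness times are gamma-distributed with mean 23.3 and SD 9.8 min, close to the midpoint (26.7 + 20.0)/2 = 23.35 and the SD of 9.69 above. Times are rounded up to the scoring step and compared by t-test. A given share of BIS subjects is signed off one step early, never before the first step.

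| Step | Share signed off early | Rejection at 0.05 | Rejection at 0.05/3 = 0.0167 (first Holm step) |
|---|---|---|---|
| 15 min | 0% | 5% | 2% |
| 15 min | 10% | 8% | 3% |
| 15 min | 20% | 20% | 10% |
| 15 min | 30% | 37–39% | 22–24% |
| 5 min | 20% | 8% | 3% |
| 5 min | 30% | 12% | 4% |

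Ranges are from repeat runs. With the 15-minute step the spurious benefit is about 2.4 min at 20% and 3.6 min at 30%; 3.6/6.7 = 54% of the earlier study's difference. With the 5-minute step it is about 0.20 × 5 = 1.0 and 0.30 × 5 = 1.5 min.

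**The case against.** The case against rests on several points, most of which stand.

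- **Scope.** A reader might infer that PACU staff score all the tested recovery endpoints. The documents do not support that. Extubation happens under the anesthetist, and emergence may occur before the PACU. Only discharge readiness is clearly a PACU endpoint among the three.
- **Timing and staff.** The synopsis starts the 15-minute assessments at anesthesia termination, and Table 5 marks the three scales under end of surgery as well as PACU. Some scores may be taken in the operating room by people who saw the titration. Since the scorer is not named, it is an inference that masking needs no extra staff.
- **Step size.** Sections 10.9.6 and 10.9.6.4 ask for the time of readiness to be recorded, and nothing says that it is rounded to the scoring grid. The larger error rates depend on the assumed 15-minute step.
- **Judgement.** Modified Aldrete is partly numeric (blood pressure and heart rate within 20%, saturation above 92%). This limits the room for bias but does not remove it. In addition, 10.9.6.4 sets the threshold at 12 of 16, while the five items in Appendix C sum to at most 5 × 2 = 10. Those passages must be reconciled; until then the printed scale does not fix the decision.
- **The earlier study.** A reader might infer that this trial dropped a protection its predecessor had. Section 4.1.3.2 says only that the study was observer-blinded, not which observer or which outcomes.
- **Disclosure.** It might also be inferred that PACU staff are told the arm. The plan does not say so; it only fails to prevent it.

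What does not fall is the gap itself: no passage masks the person who scores readiness or PAED.

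**Conclusion.** The point holds in a limited form. As written, the plan leaves one Holm-tested secondary endpoint, time to PACU discharge readiness, and the descriptive PAED comparison open to observer bias. Study success rests on end-tidal sevoflurane, which scoring does not touch, and the secondary tests are reached only if the primary is met. It would therefore be wrong to infer a threat to the primary result, or that an observed recovery benefit must be an artefact.

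The size is an assumption, not an estimate. With no true effect, 54 per arm and 20–30% of BIS subjects signed off one step early, the false-positive rate at 0.05 is about 8–12% with a 5-minute step and about 20–39% with a 15-minute step. The documents give neither the early sign-off rate nor the step. The model also assumes that every such error favours BIS and that readiness is compared with the age groups pooled. This should be corrected, but it does not undermine the trial's main conclusion.

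**What to change.** Amend Protocol 10.9.6:

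1. State that Modified Aldrete and PAED scores taken in the PACU are recorded by the usual PACU staff, who are not told the assignment.
2. Leave the study arm and BIS values out of the routine PACU handover, unless the anesthesiologist judges them clinically necessary.
3. Confirm that the sensor is removed in both arms before transfer.
4. Add one eCRF field for whether the assessor knew the arm, and report it by arm.

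The study report should state that extubation, operating-room emergence and any scores taken before PACU arrival are open-label. An analysis restricted to masked assessments should be descriptive only: it selects on something that happens after randomization and may differ between arms, so it cannot carry the conclusion.

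The cost is a small handover change and one eCRF field. Where a site cannot mask its PACU scorer without an extra assessor, record the assessment as unmasked and add no staff.
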